5.6.6 Other Safety Analyses

The proportion of subjects with any treatment-emergent report of suicidal ideation and behavior and intensity of these behaviors will be summarized. Listings from pregnancy tests will be prepared.

5.7 Other Analyses

The change from baseline in QOLIE-31 and PedsQL 4.0 Scale will be summarized.

5.8 Exploratory Analyses

Eisai Final 4.0 Confidential Page 20 of 30 May 18, 2024

5.9 Extension Phase Analyses

Efficacy Analyses

Descriptive statistics will be provided for the efficacy endpoints in the Extension Phase. Mean, standard deviation, median, minimum, and maximum will be provided for continuous endpoints and number and percentage will provide for categorical variables. In addition, plots will be used to summarize the data. Efficacy analyses will be performed similarly to the Core Study analyses and all analyses will be on the treatment duration (Core Study and Extension Phase).

Safety Analyses

All safety analyses will be performed on the Safety Analysis Set. Safety data that will be evaluated include monitoring and recording all adverse events; regular laboratory evaluation for hematology, blood chemistry, and urinalysis; periodic measurement of vital signs, weight and ECGs; and the performance of physical and neurological examinations. Safety analyses will be performed similarly to the Core Study analyses and all analyses will be on the treatment duration (Core Study and Extension Phase).

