Statistical analyses will be performed by the sponsor or designee after the study is completed, the database is locked and released, and a snapshot of the database is obtained and released. Analyses for regional submissions may be performed during the course of the study. Statistical analyses will be performed using SAS software or other validated statistical software, as required. Details of the statistical analyses will be included in a separate statistical analysis plan.

Statistical and Analytical Plans

The statistical analyses of Extension Phase data are described in this section. Further details of the analytical plan will be provided in the statistical analysis plan, which will be finalized before database lock and treatment unblinding.

Study Endpoints

- Safety and tolerability, including incidence of treatment-emergent adverse events
- PK parameters of lorcaserin in the Treatment Period
- Percent change in frequency of convulsive seizures
- Percent change in frequency of each type of seizure
- Proportion of subjects who are free from convulsive seizures
- Proportion of subjects who are seizure-free
- Percent change from baseline in frequency of clusters
- Clinical Global Impression of Change
- Change from baseline in QOLIE-31 and PedsQL 4.0 Scales

Analysis sets

Safety Analysis Set is the group of subjects who received at least 1 dose of study drug and had at least 1 postdose safety assessment in the Extension Phase.

Full Analysis Set is the group of subjects who received at least 1 dose of study drug and had at least 1 postdose seizure measurement in the Extension Phase.

Efficacy Analyses

Descriptive statistics will be provided for the efficacy endpoints in the Extension Phase. Mean, standard deviation, median, minimum, and maximum will be provided for continuous endpoints and number and percentage will provide for categorical variables. In addition, plots will be used to summarize the data.

Safety Analyses

All safety analyses will be performed on the Safety Analysis Set. Safety data that will be evaluated include monitoring and recording all adverse events; regular laboratory evaluation for hematology, blood chemistry, and urinalysis; periodic measurement of vital signs, weight and ECGs; and the performance of physical and neurological examinations. Safety analyses will be performed similarly to the Core Study analyses and all analyses will be on the treatment duration (Core Study and Extension Phase).

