5.2 Study Subjects

5.2.1 Definitions of Analysis Sets

The Safety Analysis Set is the group of subjects who received at least 1 dose of study drug and had at least 1 postdose safety assessment.

The Full Analysis Set is the group of randomized subjects who received at least 1 dose of

Eisai Final 4.0 Confidential Page 11 of 30 study drug and had at least 1 postdose primary efficacy measurement.

The PK Analysis Set is the group of all randomized subjects from whom at least measurable lorcaserin plasma concentration was obtained with associated documented dosing history.

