8 DEFINITIONS AND CONVENTIONS FOR DATA HANDLING

8.1 Efficacy: Seizure Frequency per 28 Days

Seizure frequency for convulsive seizures, total seizures, non-convulsive seizures, and per seizure type, will be based on number of seizures per 28 days, calculated during the Baseline Period and Treatment Period, as the number of seizures during each respective period divided by the number of non-missing days during each respective period, multiplied by 28.

Eisai Final 4.0 Confidential Page 21 of 30

Baseline Period Seizure Frequency: number of seizures during the screening period to the date prior to randomization, divided by the number of non-missing days, multiplied by 28.

Treatment Period Seizure Frequency: number of seizures from the date of randomization to the end of the treatment period divided by the number of non-missing days, multiplied by 28.

Endpoint Definitions:

Percent Change from Baseline = 100 * (Treatment Period – Baseline Period) / Baseline Period

For the rank ANCOVA models the ranks of Baseline Period Seizure Frequency and the ranks of Percent Change from Baseline will be used in the analyses.

```
50% Responders = 1 if percent change from baseline ≤ -50%
0 otherwise
```

Seizure freedom for convulsive seizures, non-convulsive seizures, and total seizures, will be defined two ways; 1) counting seizures only and not counting clusters and 2) counting both seizures and clusters

```
Seizure-freedom = 1 if percent change from baseline = -100%
0 otherwise
```

Convulsive seizures: The sum of seizure frequencies of hemiclonic, tonic, clonic, tonic-atonic, generalized tonic-clonic, and focal with clearly observable motor signs.

Non-convulsive seizures: The sum of all other seizure frequencies not listed under convulsive seizures.

Total seizures: The sum of seizure frequencies for all seizure types.

S-curve plots (percent change from baseline on the x-axis and cumulative proportion on the y-axis) both treatment groups, will be provided for convulsive seizures, non-convulsive seizures and total seizures.

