8.3 Definition of Visit Windows

Table 3 of the protocol presents the schedule of procedures/Assessments. The screening/baseline period is four weeks long and procedures/assessments are performed at randomization, weeks 1, 2, 4, 6, 10, and 14 of the treatment period with a follow-up of 4 weeks after end of treatment. Table 3 presents the protocol specified visits/weeks and corresponding time windows used for visit-wise analyses are presented in terms of days relative to the randomization. If more than one measurement is included in a visit window, the measurement collected closest to the scheduled date will be used in the analysis. In the case where two measurements were collected an equal number of days before and after the Scheduled Day the later of the two measurements will be used for analysis. For ECHO assessments when assessing a new or worsened event then the most severe assessment will be selected if 2 or more assessments fall within a visit window

Eisai Final 4.0 Confidential Page 23 of 30

Table 3 Visit Windows Measurements

Scheduled	Scheduled Week	Scheduled	Time Window (Days)	
1	Screening		First day of Screening	-1
2	Baseline/ Randomization	1	1	
3	1	7	2	10
4	2	14	11	17
5	4	28	18	34
6	6	42	35	48
7	10	70	49	82
8	14	98	83	101
Extension Phase				
9	15	105	102	110
10	17	119	111	125
11	20	140	126	149
12	23	161	150	169
13	26	182	170	194

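### SAP 5.9 puts extension efficacy on the combined Core and Extension duration, against its own opening sentence and Protocol Appendix 2; read literally, former placebo subjects' results mix placebo and lorcaserin time

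*SAP*

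**What the plan says.** SAP 5.9 (Extension Phase Analyses) opens its efficacy paragraph with "Descriptive statistics will be provided for the efficacy endpoints in the Extension Phase". The same paragraph ends with "Efficacy analyses will be performed similarly to the Core Study analyses and all analyses will be on the treatment duration", followed by a parenthesis naming the Core Study and the Extension Phase.

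Protocol Appendix 2 has the opening sentence under Efficacy Analyses but not the closing one. There the combined duration appears only under Safety Analyses: "Safety analyses will be performed similarly to the Core Study analyses and all analyses will be on the treatment duration". Appendix 2 also gives the Extension its own Full Analysis Set, limited to subjects who "had at least 1 postdose seizure measurement in the Extension Phase". SAP 5.2.1 lists one Full Analysis Set, for randomized subjects who received at least one dose of "study drug and had at least 1 postdose primary efficacy measurement", and no Extension version.

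SAP 8.1 defines the treatment-period seizure frequency as the "number of seizures from the date of randomization to the end of the treatment period divided by the number of non-missing days", times 28. It gives no separate frequency for the Extension. Seizure freedom is "Seizure-freedom = 1 if percent change from baseline = -100" percent. SAP 8.3 (Table 3) has Extension visit windows beginning at day 102, but its "corresponding time windows used for visit-wise analyses are presented in terms of days relative to the randomization"; it does not define a period for counting seizures.

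**The concern.** The two sentences in SAP 5.9 give different analysis periods for the same endpoints, and the second departs from the protocol. SAP Section 7, which lists changes to the planned analyses, does not mention that departure.

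The period matters because treatment changes within it for half of the design. Everyone receives lorcaserin in the Extension, and former placebo subjects switch to it after 14 weeks. The Appendix 2 efficacy objectives are to summarize how well lorcaserin works. For the placebo-lorcaserin sequence, a percent change over the combined period is an average of placebo and lorcaserin time. It understates the change on lorcaserin whenever lorcaserin works better than placebo, and seizure freedom would have to hold through the placebo weeks as well. Two programmers working from this text could report materially different Extension results for the same subjects.

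**Working it through.** **Inputs from the documents**
- Core Treatment Period: 14 weeks (SAP 3.2).
- Extension Treatment Period: 12 weeks (Protocol 9.1.3 and Appendix 2).
- Subjects randomized at termination: 22 (SAP 7), allocated 1:1 (SAP 3.2).
- Entry minimum: 4 convulsive seizures in the 4-week baseline (Protocol 9.3.1).

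**Assumptions**
- Complete diaries and completion of both periods.
- A reduction in the placebo period of 0, 10 or 20%. The documents give no value.
- Illustrative reductions on lorcaserin of 50, 75 and 100%.

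**Timeline check.** 14 + 12 = 26 weeks, and 26 × 7 = 182 days. This reproduces week 26 in SAP Figure 1 and day 182 for Visit 13 in SAP Table 3.

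**Make-up of the literal combined period, former placebo subject**
- Placebo: 14/26 = 53.8% (98 days).
- Lorcaserin: 12/26 = 46.2% (84 days).

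**Percent reduction shown over the combined period** = (14 × reduction on placebo + 12 × reduction on lorcaserin) / 26. For example, (14 × 0 + 12 × 50)/26 = 23.1.

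| Reduction on lorcaserin | Placebo 0% | Placebo 10% | Placebo 20% |
|---|---|---|---|
| 50% | 23.1% | 28.5% | 33.8% |
| 75% | 34.6% | 40.0% | 45.4% |
| 100% | 46.2% | 51.5% | 56.9% |

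At a true 50% reduction the shortfall is 26.9, 21.5 or 16.2 percentage points.

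**Seizure freedom.** The definition needs a change of exactly -100%, so one convulsive seizure in the placebo weeks disqualifies the subject. At the entry minimum of 4 per 28 days, the expected number over those 98 days is 4 × 98/28 = 14.0 with no placebo change, 14.0 × 0.9 = 12.6 with a 10% reduction, and 14.0 × 0.8 = 11.2 with a 20% reduction. A subject with no seizures at all on lorcaserin would almost certainly not be counted.

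**Subjects affected.** 22/2 = 11, so at most about 11 former placebo subjects, and only those who entered the Extension. The documents do not give that number.

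**If the sentence means that each phase is shown separately,** the Extension figure rests on 12 of 12 weeks on lorcaserin and the distortion is zero.

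**The case against.** The strongest reply is that no single sentence prescribes a pooled 26-week frequency. SAP 5.9 gives no formula. The pooled figure comes from joining it to the SAP 8.1 rule, which does not mention the Extension, and SAP 5.3.4 states the same formula for the double-blind period. The term Treatment Period is used separately for the Core and the Extension. The call for plots in 5.9 and the continuous visit numbering in Table 3 would also fit a display of both phases side by side. Programming rules and table shells are in separate documents (SAP 9 and 11). This stands: pooling is the literal reading, not the only one. It does not remove the contradiction within 5.9 or with Appendix 2, and 8.1 offers no Extension-only frequency to fall back on.

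Second, SAP Section 7 says that only descriptive statistics for primary, secondary and selected exploratory endpoints will be given. The primary and secondary endpoints visible in SAP 5.1 are Core endpoints, so extension efficacy may not be produced at all. This also stands. Section 7 neither withdraws 5.9 nor confirms it.

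Third, a reader might infer from SAP 5.2.1 that someone who left during the Core would be counted in the extension summaries. The documents do not establish this. The SAP's silence does not cancel the Appendix 2 set, and the inference needs the same literal reading of 5.9.

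**Conclusion.** The wording conflict is certain; the mixing of placebo and lorcaserin time is conditional on the literal reading. On that reading, and under the assumptions above, a 50% reduction on lorcaserin appears as 23.1 to 33.8% for a former placebo completer. On a by-phase reading nothing is distorted.

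The documents do not support a stronger claim. A reader might infer that the Core comparison or the trial's efficacy conclusion is affected. It is not: the Core analyses have their own period, and no hypothesis test uses Extension data. The lorcaserin-lorcaserin sequence contains no placebo time. Nor is the combined-duration safety sentence an error, since it is the same in both documents. What remains is a minor point about untested descriptive summaries for at most about 11 subjects, which may or may not be produced.

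**What to change.** - **SAP 5.9:** delete the combined-duration sentence for efficacy. Summarize extension efficacy over the Extension Treatment Period, by randomized sequence (lorcaserin-lorcaserin and placebo-lorcaserin), against the pre-randomization baseline. Limit any combined-period efficacy summary to the lorcaserin-lorcaserin sequence.
- **SAP 8.1:** add an Extension seizure-frequency period that starts at the first Extension dose or, if that date is not recorded, at the Visit 8 date. Visit 8, scheduled for day 98, is by SAP 3.2 also the first Extension visit, so the day-102 window in Table 3 is not the right start.
- **SAP 5.2.1:** carry over the Extension Full Analysis Set from Appendix 2.
- **SAP 7:** state whether extension efficacy is still reported.
- **Safety analyses:** no change.

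The cost is SAP wording and one derived start date, with no protocol change. Diaries are completed daily (Protocol 9.5.1.2.1). The exposure calculation in SAP 5.6.1 uses only the first and last treatment dose dates, so it does not show that the first Extension dose date is held; hence the Visit 8 fallback.

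One downside remains. The two sequences' Extension results fall at different times since starting lorcaserin: by week 26 one has had 26 weeks of it and the other 12. They should not be read as a like-for-like comparison.

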11. A clinically significant electrocardiogram (ECG) abnormality, including a marked baseline prolonged QT/correct QT interval (eg, a repeated demonstration of a corrected QT interval >460 ms)
12. Any history of clinically significant bradycardia or other clinically significant conduction abnormality
13. Any suicidal ideation with intent with or without a plan at Screening or within 6 months of Screening (ie, answering "Yes" to questions 4 or 5 on the Suicidal Ideation section of the Columbia-Suicide Severity Rating Scale [C-SSRS] or based on investigator's clinical judgment for subjects unable to be evaluated by C-SSRS)
14. Any lifetime suicidal behavior (per the Suicidal Behavior section of the C-SSRS or based on investigator's clinical judgment for subjects unable to be evaluated by C-SSRS)

15. Hypersensitivity to the study drug and any of the excipients
16. Scheduled for surgery during the study
17. Use of illegal recreational drugs
18. Currently enrolled in another clinical study or used any investigational drug or device within 4 weeks before Screening or within approximately 5 half-lives, whichever is longer.

Study Treatments

Test drug: E2023, oral, 10-mg tablets

Comparator Drug: placebo, oral tablets matching the test drug

Study drug will be taken as a suspension BID approximately 12 hours apart.

To prepare the suspension of study drug before each administration, 2 tablets (from a blister pack, assigned by interactive voice and web response system [IxRS]) will first be suspended in 10 mL of water, after which 70 mL of sugar-free Ora-Sweet Syrup will be added and the suspension mixed thoroughly. For subjects with weight <20 kg, a 20 mL aliquot of this suspension, or for subjects with weight \geq 20 kg, a 40 mL aliquot of this suspension will be taken orally and the remainder of the suspension should be discarded after each administration.

Duration of Treatment

14 weeks double-blind Treatment Period and 12 weeks open-label Extension Phase

Concomitant Drug/Therapy

Concomitant AEDs, including Epidiolex[®], initiated before Screening are allowed; the dose must remain stable during the Prerandomization and Randomization Phase.

Benzodiazepines are allowed as AEDs or rescue medication for seizure control.

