9.5.1.4.1 ADVERSE EVENTS

An AE is any untoward medical occurrence in a patient or clinical investigation subject administered an investigational product. An AE does not necessarily have a causal relationship with the medicinal product. For this study, the study drug is E2023 or placebo.

The criteria for identifying AEs in this study are:

- Any unfavorable and unintended sign (including an abnormal laboratory finding), symptom, or disease temporally associated with the use of an investigational product, whether or not considered related to the investigational product (Note: Every sign or symptom should not be listed as a separate AE if the applicable disease [diagnosis] is being reported as an AE)
- Any new disease or exacerbation of an existing disease. However, worsening of the primary disease should be captured under efficacy assessments as disease progression.
- Any deterioration in nonprotocol-required measurements of a laboratory value or other clinical test (eg, ECG or x-ray) that results in symptoms, a change in treatment, or discontinuation of study drug

- Recurrence of an intermittent medical condition (eg, headache) not present pretreatment (Baseline)
- An abnormal laboratory test result should be considered an AE if the identified laboratory abnormality leads to any type of intervention, withdrawal of study drug, or withholding of study drug, whether prescribed in the protocol or not.

All AEs, regardless of relationship to study drug or procedure, should be recorded beginning from the time the subject signs the study ICF through the last visit of the End of Treatment Phase. Refer to [Section 9.5.4.1](#) for the time period after the end of treatment for SAE collection.

Abnormal laboratory values should not be listed as separate AEs if they are considered to be part of the clinical syndrome that is being reported as an AE. It is the responsibility of the investigator to review all laboratory findings in all subjects and determine if they constitute an AE. Medical and scientific judgment should be exercised in deciding whether an isolated laboratory abnormality should be classified as an AE. Any laboratory abnormality considered to constitute an AE should be reported on the Adverse Event CRF.

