Appendix 2 Extension Phase

Study Design and Plan

The Extension Phase will consist of a Treatment Period (12 weeks) and a Follow-up Period (4 weeks). Subjects are eligible to complete the Extension Phase only if they have completed the Treatment Period of the Core Study.

All subjects will receive lorcaserin during entire Extension Phase but the dose level will be blinded during the first 6 weeks. During the first 6 weeks of the Extension Phase, subjects who received lorcaserin during the Core Study will receive the same dose of lorcaserin (the dose will remain flexible per weight category, based on clinical response and tolerability); subjects who received placebo during the Core Study will receive the target dose of lorcaserin per weight category. During the second 6 weeks of the Extension Phase, all subjects will receive lorcaserin at the maximum dose per weight category (the dose may be decreased due to tolerability reasons and increased again if tolerability improves). Addition, deletion, and dose changes to concomitant antiepileptic drugs (AEDs) are not allowed during the Treatment Period of the Extension Phase.

The Follow-up Visit will be conducted 4 weeks after the last dose of study drug for subjects who will not participate in the Extended Access Program (Study E2023-A001-405) after completion of this study.

The objectives of the Extension Phase are:

- To evaluate the safety and tolerability of lorcaserin
- To characterize the pharmacokinetics (PK) of lorcaserin and the relationship between lorcaserin plasma concentrations, efficacy, and safety
- To summarize the efficacy of lorcaserin as measured by percent change in frequency of convulsive seizures
- To summarize the efficacy of lorcaserin as measured by percent change in frequency of each type of seizure
- To summarize the efficacy of lorcaserin as measured by proportion of subjects who are free from convulsive seizures
- To summarize the efficacy of lorcaserin as measured by proportion of subjects who are seizure-free
- To summarize the efficacy of lorcaserin as measured by percent change in frequency of clusters
- To summarize the efficacy of lorcaserin as measured by Clinical Global Impression of Change
- To summarize the efficacy of lorcaserin as measured by on quality of life

Schedule of Procedures/Assessments

Table 4 presents the Schedule of Procedures/Assessments for the Extension Phase.

Table 4 Schedule of Procedures/Assessments in Study E2023-A001-304: Extension Phase

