5.6.2 Adverse Events

The AE verbatim descriptions (investigator terms from the CRF) will be classified into standardized medical terminology using the Medical Dictionary for Regulatory Activities (MedDRA). AEs will be coded to the MedDRA (Version 23 or higher) lower level term closest to the verbatim term. The linked MedDRA PT and primary system organ class (SOC) are also captured in the database.

A TEAE is defined as an AE that emerges during treatment up to the subject's last dose or up to 28 days after the subject's last dose for subjects who do not enter the extension phase (for core study analysis) or do not enter Study E2023-A001-405 (for extension phase analysis), having been absent at pretreatment (Baseline) or

- Reemerges during treatment, having been present at pretreatment (Baseline) but stopped before treatment, or
- Worsens in severity during treatment relative to the pretreatment state, when the AE is continuous.

Only those AEs that are treatment-emergent will be included in summary tables. All AEs, treatment-emergent or otherwise, will be presented in subject data listings.

The TEAEs will be summarized by treatment group. The incidence of TEAEs will be reported as the number (percentage) of subjects with TEAEs by SOC and PT. A subject will be counted only once within an SOC and PT, even if the subject experienced more than 1 TEAE within a specific SOC and PT. The number (percentage) of subjects with TEAEs will also be summarized by maximum severity (mild, moderate, or severe).

Eisai Final 4.0 Confidential Page 18 of 30

The number (percentage) of subjects with TEAEs will also be summarized by relationship to study drug (Yes [related] and No [not related]).

The number (percentage) of subjects with treatment-related TEAEs will be summarized by SOC and PT. Treatment-related TEAEs include those events considered by the investigator to be related to study treatment. The number (percentage) of subjects with treatment-related TEAEs will also be summarized by maximum severity (mild, moderate, or severe).

The number (percentage) of subjects with TEAEs leading to death will be summarized by MedDRA SOC and PT. A subject data listing of all AEs leading to death will be provided.

The number (percentage) of subjects with treatment-emergent SAEs will be summarized by MedDRA SOC and PT for each treatment group. A subject data listing of all SAEs will be provided.

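### Extension adverse-event tables count former placebo subjects from their first placebo dose, so they cannot show which events emerged on lorcaserin

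*SAP*

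**What the plan says.** SAP 5.9 sets the window for the Extension safety analyses: "Safety analyses will be performed similarly to the Core Study analyses and all analyses will be on the treatment duration (Core Study and Extension Phase". The same sentence stands under Safety Analyses in Protocol Appendix 2. Both also say that these analyses follow the Core ones, and SAP 5.6.2 gives the Core method: "The TEAEs will be summarized by treatment group" and "A subject will be counted only once within an SOC and PT, even if the subject experienced more than 1 TEAE within a specific SOC".

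The start of counting follows from four places:
- Protocol 9.5.1.4.1: "the study drug is E2023 or placebo".
- SAP 5.6.1: duration of treatment runs from the first to the last treatment dose.
- SAP 5.6.2: emergence is judged against the pretreatment state. The definition mentions the extension analysis, but only to set where the window ends.
- SAP 8.2: the safety baseline is the last assessment before randomisation.

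The treatment changes at the end of the Core for half of the design. Protocol Appendix 2 says "All subjects will receive lorcaserin during entire Extension Phase", and that "subjects who received placebo during the Core Study will receive the target dose of lorcaserin per weight category".

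Neither document restarts emergence at the first lorcaserin dose or defines the columns of the Extension tables.

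**The concern.** The first Extension objective in Protocol Appendix 2 is the safety and tolerability of lorcaserin. Former placebo subjects are informative for it because their first exposure to the drug falls inside the Extension. Under the combined window, their row in a TEAE table answers a different question: whether the term ever occurred on placebo or lorcaserin.

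The count per term carries no onset period, so the table cannot be taken apart afterwards. A subject who had somnolence, say, in placebo week 3 and again in lorcaserin week 2 appears once, and the event on drug leaves no trace in the count.

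SAP 7 records that the study was terminated with 22 subjects randomised. It reduces the efficacy and PK work but does not withdraw the safety summaries. With 1:1 allocation, former placebo subjects could be up to about half of everyone exposed to lorcaserin. If all 22 completed, they would supply 12/(26 + 12) = 12/38 = 32% of lorcaserin person-time.

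**Working it through.** **Inputs from the documents.** Phase lengths are in the protocol synopsis: "14 weeks double-blind Treatment Period and 12 weeks open-label Extension Phase". SAP Table 3 puts Visit 8 at Day 98 and Visit 13 at Week 26, Day 182. These agree: 14 × 7 = 98, 14 + 12 = 26 and 26 × 7 = 182. Allocation is 1:1 (SAP 3.2).

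**Assumed inputs.** The documents give no adverse-event rates. I assume constant hazards, full follow-up and three pairs of 14-week incidence for one term, pP on placebo and pL on lorcaserin.

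**Step 1, time shares for a completer.** Former placebo: 14/26 = 53.8% placebo and 12/26 = 46.2% lorcaserin. Randomised to lorcaserin: 26/26 lorcaserin. If both arms enter equally and are pooled, 14/52 = 26.9% of the time in the column is placebo.

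**Step 2, incidence formulas.**
- A, lorcaserin for 26 weeks: 1 − (1 − pL)^(26/14)
- U, hypothetical unmixed placebo for 26 weeks: 1 − (1 − pP)^(26/14)
- M, former placebo on the combined window: 1 − (1 − pP)(1 − pL)^(12/14)
- N, former placebo, lorcaserin weeks only: 1 − (1 − pL)^(12/14)
- Share of counted former placebo subjects whose first event was on placebo: pP/M
- Share with a lorcaserin-period event hidden by an earlier placebo one: pP × N (periods independent)

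| pP / pL | A | U | M | N | A/U | A/M | pP/M | pP × N |
|---|---|---|---|---|---|---|---|---|
| 10% / 30% | 48.4% | 17.8% | 33.7% | 26.3% | 2.73 | 1.44 | 30% | 2.6% |
| 10% / 20% | 33.9% | 17.8% | 25.7% | 17.4% | 1.91 | 1.32 | 39% | 1.7% |
| 20% / 40% | 61.3% | 33.9% | 48.4% | 35.5% | 1.81 | 1.27 | 41% | 7.1% |

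Ratios use unrounded values; the first is 0.4844/0.1777 = 2.73. A/U is the right comparator for A/M because both cover 26 weeks.

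**Step 3, check on the rate scale.** With a true lorcaserin-to-placebo rate ratio R, columns by randomised arm show 26R/(14 + 12R). R = 1.5 gives 39/32 = 1.22, R = 2 gives 52/38 = 1.37, and R = 3 gives 78/50 = 1.56. R = 1 stays at 1.

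**Step 4, what each labelling does.**
- *Randomised arm:* lorcaserin-onset events in former placebo subjects fall under placebo, and a true difference is diluted as above.
- *One pooled lorcaserin column:* placebo-onset events are attributed to lorcaserin. The direction depends on the measure. The pooled rate relative to placebo is (14 + 38R)/52, so R = 2 appears as 90/52 = 1.73. But crude 26-week incidence set beside 14-week Core placebo incidence is inflated: with R = 1 and 20% at 14 weeks it is 1 − 0.8^(26/14) = 33.9%.
- *Sequence labels (lorcaserin/lorcaserin, placebo/lorcaserin):* the groups are named correctly, but the second column still mixes the two periods.

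**The case against.** A reader might infer that the trial's harm comparison is biased whatever the columns are called. The documents do not support that. The randomised comparison is the 14-week Core analysis, which SAP 5.6.2 keeps apart from the extension analysis, and it is untouched. Comparison with placebo is not an Extension safety objective, and the safety output is descriptive. Dilution toward no difference arises only with columns by randomised arm, and only if the rates differ.

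A reader might also set the combined-window ratios against the 14-week Core ratios of 3.0, 2.0 and 2.0. That exaggerates the fall, because part of it comes only from the longer window.

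Other points have weight. Table shells and derivation rules are in separate documents (SAP 11 and 9) and may define the columns. All adverse events are to be listed by subject, so timing can be reconstructed by hand. The number entering the Extension is not given. With 11 former placebo subjects and the 10%/30% assumption, about 0.10 × 11 = 1.1 subjects per term would have a first event on placebo, and 0.026 × 11 = 0.3 would have a hidden one.

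These points limit the size and reach of the problem but do not remove it. The combined window is stated in both documents, and the TEAE definition was adapted for the extension analysis only at its end. Column labels do not split a combined onset window. Listings show that the data exist, but they do not make the table answer the Extension objective.

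**Conclusion.** The point holds for the Extension TEAE incidence tables. For former placebo subjects who complete, 14 of 26 counted weeks are placebo, and the planned count cannot isolate what emerged on lorcaserin. That conclusion rests on the text alone.

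The numerical size rests on constant hazards, full follow-up and assumed incidences. Across the three pairs, 30% to 41% of counted former placebo subjects had their first event on placebo. If columns follow randomised arm, 26-week ratios of 2.73, 1.91 and 1.81 become 1.44, 1.32 and 1.27. By-visit summaries of laboratory values, vital signs and ECGs can be separated with the SAP 8.3 visit windows, so the problem lies mainly in adverse-event incidence. The change should be made, but the Core safety conclusions do not depend on it.

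**What to change.** In SAP 5.9 and Protocol Appendix 2, replace the combined-duration sentence as it applies to adverse events:

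- For the Extension and overall lorcaserin tables, a TEAE is an event that emerges or worsens on or after the first lorcaserin dose. That is the first Core dose for subjects randomised to lorcaserin and the first Extension dose for former placebo subjects.
- Emergence and worsening are judged against the state just before that dose, and the once-per-term count applies within that window.
- Tables show lorcaserin/lorcaserin and placebo/lorcaserin columns, each with its exposure duration.
- Events in the placebo weeks stay in the Core table.

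Exposure-adjusted rates are optional. They would not make the columns fully comparable: the protocol's Extension safety set holds only subjects dosed and assessed in the Extension, and the dose rules for the first 6 weeks differ between the two sequences.

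The cost is a wording change and one extra treatment-emergent flag from existing onset and dosing dates, with no new data. The downside is smaller counts in the placebo/lorcaserin column.
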